7.5.1.2 Overall Survival

Overall Survival (OS) is defined as the time from the date of randomization to death from any cause. Patients will be followed until their date of death, loss to follow-up, or withdrawal of consent for further follow-up for survival. Patients who are lost to follow-up will be censored at their last known alive date. Patients who do not have date of death at final database lock will be censored at their last known alive date. Patients who do not have any follow-up since randomization will be censored on the date of randomization.

The primary analysis for OS will use the ITT I/P-risk Population and the ITT All-risk Population.

Two-sided alpha levels of 0.01 and 0.0472 are allocated to the interim and final analyses, respectively, to control the overall type I error rate at 0.05 level for the primary OS analysis in the IMDC Intermediate- or Poor-risk and the IMDC All-risk Populations assuming ORR is significant in both the IMDC Intermediate- or Poor-risk and the IMDC All-risk Populations. If ORR is not statistically significant in either population, an overall alpha of 0.049 will be used for OS where 0.01 will be spent at the interim analysis and 0.0462 will be spent at the final analysis. Within each analysis, OS in the IMDC Intermediate- or Poor-risk Population will be tested first, and only when it is statistically significant, can OS in the IMDC All-risk Population be tested at the same level.

Overall survival will be compared between the treatment groups at the interim and final analyses, using the stratified logrank test. The stratification factors will be the same as those used in the analysis of ORR (IMDC prognostic score and TKI choice) as defined in Section 6.5. At the final analysis, the primary analysis of OS to claim statistical significance will be based on the weighted combination test of the stratified logrank test statistic with pre-specified weights of $\sqrt{2/3}$ and $\sqrt{1/3}$ (Lehmacher and Wassmer, 1999). The details are included in Appendix 15.1. The conventional stratified logrank test with equal weights for every patient will be conducted as a sensitivity analysis at the final analysis.

A stratified Cox proportional hazards model with treatment as the single covariate will be used to estimate the hazard ratio and corresponding 95% CI. The stratification factors will be the same as those used in the analysis of ORR (IMDC prognostic score and TKI choice) as defined in Section 6.5. The Kaplan-Meier method will be used to further summarize OS, including Kaplan-Meier curves, and medians with corresponding 95% CIs. The OS rates at fixed timepoints (e.g. 12 months, 24 months, depending on minimum follow-up) will also be estimated along with their corresponding 95% CIs.

A sensitivity analysis for OS using an unstratified logrank test will also be performed. The hazard ratio associated with treatment will be presented along with the corresponding 95% CI.

The status of patients who are censored in the OS Kaplan-Meier (KM) analysis will be tabulated for each treatment group using the following categories:

- On-study (on-treatment, in follow-up)
- Off-study (lost to follow-up, withdraw consent, never treated)

The OS for patients who received sunitinib and the OS for patients who received NKTR-214 and nivolumab will be summarized and compared using the Kaplan-Meier method. The median and 95% CI will be presented for each treatment group, and the stratified logrank test will be performed. The stratification factor IMDC prognostic score will be used.

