OS in IMDC intermediate- or poor-risk population and IMDC all-risk population	
Overall survival (OS) is defined as the time between the date of randomization and the date of death due to any cause. Patients who do not have a date of death will be censored on the last date for which a patient was known to be alive. The OS analysis will use the IMDC intermediate or poor risk and IMDC all-risk subsets of the ITT population.
 
The overall Type I error rate is 0.05 for the primary OS analysis in IMDC intermediate- or poor-risk and IMDC all-risk populations assuming ORR is significant in both IMDC intermediate- or poor-risk and IMDC all-risk populations. The alpha of 0.01 will be spent at interim and the remaining alpha of 0.04 will be spent at final analysis corresponding to the statistical significance level of 0.047 calculated based on the correlation of the interim and final CHW test statistic. If ORR is not statistically significant in either population, an overall alpha of 0.049 will be used for OS where 0.01 will be spent at interim and the remaining alpha of 0.039 will be spent at final analysis corresponding to the statistical significance level of 0.046. Within each analysis, OS in IMDC intermediate- or poor-risk population will be tested first, and only when it is statistically significant, OS in IMDC all-risk population can be tested at the same level.
 
At the final analysis, the primary analysis of OS to claim statistical significance will be based on the CHW version of the stratified log-rank test statistic with pre-specified weights of $\sqrt{2/3}$ and $\sqrt{1/3}$ (Cui Hung Wang, 1999). Statistical significance level of 0.047 and 0.046 depending on the statistical significance of ORR is calculated based on the correlation between the interim and final CHW test statistics. The conventional stratified log-rank test with equal weights for every patient will be conducted as a sensitivity analysis. Details will be provided in the SAP.
 
A stratified Cox proportional hazards model with treatment as the single covariate will be used to estimate the hazard ratio and corresponding 95% CI. The Kaplan-Meier method will be used to further summarize OS, including Kaplan-Meier curves, and medians with corresponding 95% CIs. The OS rates at 12 and 24 months will also be estimated.

Key Secondary	

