7.5.1.1 Objective Response Rate

Objective response rate (ORR) is defined as the number of randomized patients who achieve a best overall response of confirmed complete response (CR) or confirmed partial response (PR) based on BICR assessments (using mRECIST 1.1 criteria) divided by the number of all randomized patients. Best Overall Response (BOR) is defined as the best response, as determined by the BICR, recorded between the date of randomization and the date of objectively documented progression per mRECIST 1.1 criteria or the date of subsequent anti-cancer therapy (including tumor-directed radiotherapy and tumor-directed surgery), whichever occurs first. For patients without documented progression or subsequent anti-cancer therapy, all available response designations will contribute to the BOR determination. Confirmation of response is required at least 4 weeks after the initial response. A Best Overall Response of SD requires a minimum of 56 days on study from randomization to the date of the first imaging assessment.

The primary analysis is based on the ORR I/P-risk Population and the ORR All-risk Population. The ORR will be compared between treatment arms using a Cochran-Mantel Haenszel (CMH) test stratified by the stratification factors for analysis (IMDC prognostic score and TKI choice) at a 0.001 alpha level. The ORR difference between the two treatment arms with its 95% and 99.9% confidence interval (CI) will be calculated using CMH methodology and adjusted by the same stratification factors. The ORR and its corresponding 95% exact CI will also be calculated by Clopper-Pearson method (Clopper and Pearson, 1934) for each arm. The number and percentage of patients in each category of BOR per BICR (complete response [CR], partial response [PR], stable disease [SD], progressive disease [PD], or not evaluable [NE]) will be presented, by treatment arm.

The ORR per investigator assessment will also be analyzed as a sensitivity analysis, following the same approach as above. The ORR concordance rate will be computed as the frequency with which the investigator's assessment and BICR's assessment agree on classification of a patient as responder versus non responder.

The ORR for patients who received sunitinib and the ORR for patients who received NKTR-214 and nivolumab will be summarized and compared using the CMH test stratified by the stratification factor IMDC prognostic score.

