15.0 APPENDIX

15.1 The Logrank Test for OS Analysis

Let T_1 denote the interim logrank test statistic with d_1 number of events and T_2 denote the logrank test statistic based on the cumulative data at final analysis with adapted d_2^* number of events. Then we calculate the incremental test statistic as following:

$$\tilde{T}_2^* = \frac{\sqrt{d_2^*}T_2 - \sqrt{d_1}T_1}{\sqrt{d_2^* - d_1}}.$$

The final combination test statistic (Lehmacher and Wassmer, 1999) with weight $\sqrt{\frac{2}{3}}$ and $\sqrt{\frac{1}{3}}$ can be written as $T_2^* = \sqrt{\frac{2}{3}}T_1 + \sqrt{\frac{1}{3}}\tilde{T}_2^*$. The overall Type I error rate is the probability of rejecting OS at either interim or final analysis under the null that there is no difference in survival between the treatment and control group (denoted as H_0). The critical value for the interim analysis is denoted as $\frac{z_{0.01}}{2} = \Phi^{-1}(1 - \frac{0.01}{2})$ (where Φ denotes the CDF for standard normal distribution) as two-sided 0.01 level of alpha is spent at this time. The critical value c for the final analysis is calculated so that the overall type I error rate is maintained at 0.049 (two-sided) or 0.0245 (one-sided). The probability can be calculated as follows:

$$0.0245 = P_{H_0}(T_1 > z_{0.01/2} \text{ or } T_2^* > c) = P_{H_0}(T_1 > z_{0.01/2}) + P_{H_0}(T_1 \leq z_{0.01/2} \text{ and } T_2^* > c)$$

Therefore, we need to find c such that $P_{H_0}(T_1 \leq \frac{z_{0.01}}{2} \text{ and } T_2^* > c) = 0.0195$. Because T_1 and T_2^* asymptotically follows standard normal distribution with correlation $\sqrt{\frac{2}{3}}$ (Wassmer, 2006), the critical value c can be found to be $z_{0.0231}$. This implies that the significant p-value will be 0.0231 (one-sided) or approximately 0.0462 (two-sided).

With similar arguments, if the overall type I error rate is to be maintained at 0.05 (two-sided) or 0.025 (one-sided), the nominal alpha for OS final analysis with weighted combination test will be 0.0236 (one-sided) or approximately 0.0472 (two-sided).

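### The planned 95% Cox intervals for the OS hazard ratio do not correspond to the tests that decide OS significance, at the interim or at the final analysis

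*SAP*

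**What the plan says.** **Decision rule.** SAP 7.5.1.2 sets the OS levels: "Two-sided alpha levels of 0.01 and 0.0472 are allocated to the interim and final analyses" when ORR has succeeded in both populations. Otherwise "0.01 will be spent at the interim analysis and 0.0462 will be spent at the final analysis". On the last look the section states: "the primary analysis of OS to claim statistical significance will be based on the weighted combination test of the stratified logrank test statistic". The weights are √(2/3) and √(1/3). The conventional equal-weight stratified logrank test is kept as a sensitivity analysis. SAP Appendix 15.1 derives the final levels.

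**Estimation.** The same section says: "A stratified Cox proportional hazards model with treatment as the single covariate will be used to estimate the hazard ratio and corresponding 95% CI". Protocol 9.5 agrees: the stratified Cox model "will be used to estimate the hazard ratio and corresponding 95% CI". An unstratified sensitivity HR also gets a 95% interval. The remaining OS intervals are 95% intervals for Kaplan-Meier medians and survival rates. No 99% interim interval, repeated interval or interval from the combination statistic is planned.

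**Contrast.** For ORR, tested at 0.001, SAP 7.5.1.1 and Protocol 9.5 report both a 95% and a 99.9% interval for the difference. Protocol 2.3.1 also quotes earlier trials with intervals set to the test level, such as a 99.8% interval beside an alpha of 0.002.

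**The concern.** OS is a primary endpoint, and readers treat an interval that excludes 1 as equivalent to a significant test. Here the two can differ for two reasons.

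- At the interim the test is at 0.01 and the interval is at 95%.
- At the final analysis the test gives the interim data a fixed weight of 2/3 whatever the final event count, while the Cox model weights every event equally and takes no account of the earlier look. The Cox interval therefore pairs with the test that the SAP treats as a sensitivity analysis, not with the primary one.

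If test and interval conflict, the plan does not say which interval accompanies the claim, and that choice would be made after the data are seen. In addition, an HR reported because OS crossed at the interim has been selected for being extreme.

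**Working it through.** **Inputs.** Interim at 156 events or more in the intermediate- or poor-risk population (SAP 10.0; 156 used here). Final events between 200 and 308, design HR 0.63 (SAP 6.2.2). 1:1 allocation (SAP 5.1). Levels and weights as above. HRs of 0.70 and 0.75 are added to show the range.

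**Approximation.** With d events the logrank statistic, positive when it favours the experimental arm, is normal with mean −ln(HR)·√d/2 and variance 1. The standard error of ln HR is 2/√d. The Cox Wald statistic is taken as equal to the logrank statistic.

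**1. The plan's own levels.** With correlation √(2/3), solve P(T1 ≤ z(0.005), T2* > c) = 0.0195. This gives c = 1.9936, one-sided 0.0231, two-sided 0.0462, as in Appendix 15.1. With 0.02 in place of 0.0195 the one-sided level is 0.0236 and the unrounded two-sided level 0.04725, against 0.0472 stated. Both reproduce.

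**2. Interim.** The critical HR is exp(−2z/√156):

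- 95% interval excludes 1: exp(−2 × 1.960/12.49) = 0.731
- significant at 0.01: exp(−2 × 2.576/12.49) = 0.662

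| True HR | Mean of T1 | P(0.662 < observed HR < 0.731) | P(OS crosses) |
|---|---|---|---|
| 0.63 | 2.885 | 20.1% | 62% |
| 0.70 | 2.227 | 24.2% | 36% |
| 0.75 | 1.797 | 21.7% | 22% |

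Only this direction is possible: p below 0.01 forces the 95% interval to exclude 1. Example: z = 2.3 (p = 0.021, not significant) gives HR 0.69, 95% interval 0.51 to 0.95, 99% interval 0.46 to 1.05.

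**3. Final.** Let U be the independent increment after the interim and d2 the final event count. The test uses T2* = √(2/3)·T1 + √(1/3)·U. The Cox interval follows T2 = √(156/d2)·T1 + √(1 − 156/d2)·U. The two coincide only when 156/d2 = 2/3, that is at 234 events. At 200 the fraction is 0.78 and at 308 it is 0.51. Among trials that did not cross at the interim, over both final levels:

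| d2 | True HR | Interval excludes 1, test fails | Test passes, interval includes 1 | Total |
|---|---|---|---|---|
| 200 | 0.63 | 2.8–3.0% | 1.2–1.4% | 4.1–4.3% |
| 200 | 0.70 | 3.2–3.4% | 1.5–1.7% | 4.8–5.0% |
| 200 | 0.75 | 2.9–3.2% | 1.5–1.7% | 4.6–4.7% |
| 234 | 0.63–0.75 | 0.7–1.6% | 0 | 0.7–1.6% |
| 308 | 0.63 | 1.4–1.5% | 0.3% | 1.8% |
| 308 | 0.70 | 3.4–3.6% | 0.8–0.9% | 4.3–4.5% |
| 308 | 0.75 | 4.4–4.6% | 1.2–1.3% | 5.7–5.8% |

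As a share of all trials, the totals at 200 and 308 events run from 0.7% to 4.6%.

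**4. What a matched interval does.** Write S for the observed T2* and c for its critical value. Inverting gives ln HR = (−S ± c)/k, with k = √(2/3)·√156/2 + √(1/3)·√(d2 − 156)/2, which is 8.658 at d2 = 308. Level 0.0472:

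- T1 = 2.4, U = 0.2: S = 2.075, p = 0.038, significant. Cox 95% interval 0.648 to 1.013; inverted interval 0.63 to 0.99.
- T1 = 0.8, U = 2.1: S = 1.866, p = 0.062, not significant. Cox 95% interval 0.634 to 0.990; inverted interval 0.64 to 1.01.

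**5. Estimate after an interim crossing.** Averaging over T1 > 2.576, the mean Cox HR is about 0.57 for a true 0.63, with the 95% interval covering the truth in about 96% of those trials. For a true 0.75 the mean is about 0.61 and coverage about 89%.

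**The case against.** The strongest reply is that the decision rule is unambiguous. The SAP ties the significance claim to the combination test and uses the Cox model only to estimate, so the interval decides nothing. That stands. A reader might infer that the mismatch inflates the false-positive rate; the documents do not support this, since Appendices 15.1 and 15.3 control error without reference to any interval and the levels reproduce.

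Second, the 20 to 24% arises when OS misses at the interim. The trial then continues, and interim data are held by the DMC under confidentiality provisions (SAP 11.0). The documents do not say that a non-significant interim OS interval would be released. This lowers the harm but does not remove it. ORR is formally tested at the same look, and SAP 15.3.1 allows an efficacy claim in the intermediate- or poor-risk population while all-risk OS misses 0.01.

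Third, a reader might infer that interval and test contradict each other freely in both directions. They do not: a significant test with an interval including 1 can arise only at the final analysis, and in under 2% of continuing trials.

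Fourth, a reader might infer that the ordinary interval is generally poor after an interim crossing. At the design HR of 0.63 its coverage is about 96%; the shortfall appears at weaker effects such as 0.75, where only 22% of trials cross.

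Finally, the same remedy might seem to carry over to PFS. It does not: PFS is tested with Fleming-Harrington (0,1) weights, and inverting that combination gives no interval for the ordinary Cox HR.

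**Conclusion.** The concern holds as a reporting and estimation gap for a primary endpoint. No planned OS HR interval matches the test that decides OS. The larger mismatch is at the interim: a 20 to 24% chance, at HRs of 0.63 to 0.75, that the 95% interval excludes 1 while OS is not significant. At the final analysis the mismatch is small, about 1.8 to 5.8% of continuing trials at the two event limits and 0.7 to 1.6% at 234 events.

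These figures assume the normal approximation, proportional hazards, exactly 156 interim events and a final count fixed in advance. The real adaptation rule is in a closed appendix to the DMC charter; it would change the final frequencies but not the fact that the intervals are unmatched. The figures are for the intermediate- or poor-risk population. The all-risk population has the same structure with different event counts, which were not evaluated.

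**What to change.** In SAP 7.5.1.2, for both populations:

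- **Interim:** add a 99% interval for the OS HR.
- **Final:** add the interval obtained by inverting the combination statistic at the level actually used: 95.38% (1 − 0.0462) or 95.28% (1 − 0.0472). Name it as the interval that accompanies the primary claim.
- **Cox HR and 95% interval:** keep them, labelled descriptive.
- **Interim crossing:** state that the reported HR then tends to overstate the effect. The 99% interval does not correct this. A median-unbiased estimate is optional and would need a pre-specified ordering of outcomes across the two looks.
- **PFS:** make no parallel change, or at most show the Cox interval at the PFS alpha level as descriptive.

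Protocol 9.5 can refer to the SAP for these intervals. The cost is SAP wording, one extra calculation per OS analysis and slightly wider intervals. Design, event numbers and alpha do not change.

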7.5.2 Efficacy Analysis of Key Secondary Endpoint

The key secondary endpoint of PFS by BICR will be tested hierarchically given the statistical significance of OS. Statistical test will be two-sided with a type I error rate of 0.05 if both ORR by BICR and OS are significant in both the IMDC Intermediate- or Poor-risk and the IMDC All-risk Populations; the type I error rate will be 0.049 if OS (but not ORR by BICR) is significant in both the IMDC Intermediate- or Poor-risk and the IMDC All-risk Populations.

The PFS interim and final analysis will be conducted at the same time as the OS interim and final analyses. Two-sided alpha levels of 0.03 and 0.0335 are allocated to the PFS in the interim and final analyses, respectively, to control the overall type I error rate at two-sided 0.05. If the overall type I error rate is to be controlled at two-sided 0.049, two-sided alpha levels of 0.03 and 0.0323 will be allocated to the PFS interim and final analyses. Details are provided in [Appendix 15.2](#).

7.5.2.1 Progression-Free Survival

The definition for PFS accounts for subsequent anti-cancer therapy by censoring at the last evaluable tumor assessment on or prior to the date of subsequent anti-cancer therapy. Clinical deterioration in the absence of unequivocal evidence of progression per mRECIST 1.1 is not considered progression for purposes of determining PFS by BICR. PFS rates by BICR at fixed time points (e.g. 6 months, depending on the minimum follow-up) are defined as the probability that a patient has not progressed and is alive at time T following randomization.

The definition of PFS (PFS truncated at subsequent anti-cancer therapy) is defined as the time between the date of randomization and the date of first documented tumor progression based on BICR assessments per mRECIST v1.1, or death due to any cause, whichever occurs first, prior to subsequent anti-cancer therapy.

Patients who die without a reported progression will be considered to have progressed on the date of their death. The following censoring rules will be applied for the primary definition of PFS:

- Patients who did not have any on study tumor assessments and did not die will be censored on their date of randomization.
- Patients who did not receive subsequent anti-cancer therapy, did not progress and did not die will be censored on the date of their last evaluable tumor assessment.
- Patients who received subsequent anti-cancer therapy prior to documented progression or death will be censored at the date of the last evaluable tumor assessment conducted on or prior to the date of initiation of the subsequent anti-cancer therapy.
- Patients who received subsequent anti-cancer therapy without documented progression or death will be censored at the date of the last evaluable tumor assessment conducted on or prior to the initiation of the subsequent anti-cancer therapy.

The potential of a delayed effect in immunotherapy interventions may cause a late separation in the PFS Kaplan-Meier curves and non-proportional hazards may be observed, as was seen for PFS in the Checkmate-214 study (Motzer 2018b). Thus, the primary analysis of PFS will account for the expected delayed effect and compare the two treatment arms via a stratified weighted logrank test (Harrington and Fleming 1982). The two-sided stratified weighted logrank p-value will be reported using G ($\rho = 0, \gamma = 1$) weights. The stratification factors will be the same as those used in the analysis of ORR (IMDC prognostic score and TKI choice) as defined in Section 6.5. At the final analysis, the primary analysis of PFS to claim statistical significance will be based on the weighted combination test of the stratified weighted logrank test statistic with pre-specified weights of $\sqrt{2/3}$ and $\sqrt{1/3}$ (Lehmacher and Wassmer, 1999). The details are presented in the Appendix.

The estimate of the PFS hazard ratio between treatment groups will be calculated using a stratified Cox proportional hazards model, with treatment as the sole covariate. The stratification factors will be the same as those used in the analysis of ORR (IMDC prognostic score and TKI choice) as defined in Section 6.5. Ties will be handled using the exact method. A two-sided 95% CI for the hazard ratio will also be presented. The Kaplan-Meier method will be used to further summarize PFS, including Kaplan-Meier curves, and medians with corresponding 95% CIs.

For the primary analysis of PFS, the censoring methods described in Table 3 will be used.

The conventional stratified logrank test with equal weights for every patient will be conducted as a sensitivity analysis.

The source of PFS event (progression or death) will be summarized by treatment group.

The status of patients who are censored in the PFS KM analysis will be tabulated for each treatment group using the following categories:

- On-study (on-treatment, in follow-up)
- Off-study (lost to follow-up, withdraw consent, never treated)
- No baseline tumor assessment
- No on-study tumor assessment and no death
- Received subsequent anticancer therapy

PFS per investigator assessment will also be analyzed as a sensitivity analysis. The PFS by investigator will be defined as in Table 3, and it will be analyzed in the same approach following the primary definition of PFS by BICR.

Table 3: PFS Primary Analysis: Date of Progression or Censoring

Situation	Date of Disease Progression or Censoring	Outcome
No baseline tumor assessments*	Date of randomization	Censored
No on study tumor assessments and no death*	Date of randomization	Censored
Subsequent anti-cancer therapy started without death or progression per mRECIST v1.1 reported prior or on the same day	Date of last evaluable tumor assessment per mRECIST v1.1 showing no evidence of disease progression prior to or on the date of initiation of the subsequent anti-cancer therapy	Censored
No progression and no death, and no subsequent anti-cancer therapy started	Date of last evaluable tumor assessment per mRECIST v1.1 showing no evidence of disease progression	Censored
Documented progression per mRECIST v1.1 and no subsequent anti-cancer started before	Date of the first documented progression per mRECIST v1.1 (excludes clinical progression)	Progressed
Death without progression per mRECIST v1.1 and no subsequent anti-cancer therapy started before	Date of death	Progressed

* Tumor assessments and death if any, occurring after start of subsequent anti-cancer therapy are not considered.

A sensitivity analysis of PFS accounting for two or more missing tumor assessments prior to PFS event (death or documented progression) will be conducted. A patient is considered to have two or more missing tumor assessments if the elapsed time between the PFS event and the last assessment prior to the event is greater than the time interval of two scheduled scans + 14 days (e.g., 18 weeks + 14 days if two missing tumor assessments happened before Week 54). Patients who had PFS events immediately after two or more missed tumor assessments will be censored at the date of last tumor assessment prior to the missed visits.

